## 10.10. Appendix 10: Abbreviations

The following is a list of abbreviations that may be used in the protocol.

Abbreviation	Term
abs	absolute
ADL	activity/activities of daily living
AE	adverse event
AIDS	acquired immunodeficiency syndrome
AKI	acute kidney injury
ALT	alanine aminotransferase
AST	aspartate aminotransferase
AUC	area under the curve
AUC 24	area under the concentration-time curve over 24 hours
AUC inf	area under the concentration-time curve to infinity
AUC last	area under the plasma concentration-time profile from time 0 to the time of the last quantifiable concentration
AUC tau	area under the concentration-time curve at steady state over the dosing interval tau
AV	atrioventricular
AxMP	auxiliary medicinal product
BA	bioavailability
BBS	Biospecimen Banking System
BE	bioequivalence
β-hCG	β-human chorionic gonadotropin
BMI	body mass index
BP	blood pressure
bpm	beats per minute
BUN	blood urea nitrogen
CFR	Code of Federal Regulations
CI	confidence interval
CIOMS	Council for International Organizations of Medical Sciences
CK	creatinine kinase
CKD-EPI	chronic kidney disease epidemiology
CL	clearance
C last	last quantifiable concentration
CL/F	apparent clearance
C max	maximum observed concentration
CO 2	carbon dioxide (bicarbonate)
COVID-19	coronavirus disease 2019
CRF	case report form
CRO	contract research organization
CRU	clinical research unit
CSR	Clinical Study Report

Abbreviation	Term
CT	clinical trial
CTCAE	Common Terminology Criteria for Adverse Events
CTIS	Clinical Trial Information System
CTMS	Clinical Trial Management System
%CV	percent coefficient of variation
CV	coefficient of variation
CYP	cytochrome P450
DCT	data collection tool
DDI	drug-drug interaction
DICI	drug-induced cholestasis index
DIKI	drug-induced kidney injury
DILI	drug-induced liver injury
EC	ethics committee
ECC	emergency contact card
ECG	electrocardiogram or electrocardiography
eCrCl	estimated creatinine clearance
eCRF	electronic case report form
EDB	exposure during breastfeeding
E-DMC	External Data Monitoring Committee
EDP	exposure during pregnancy
EFD	embryo-fetal development
eGFR	estimated glomerular filtration rate
eSAE	electronic serious adverse event
ET	early termination
EU	European Union
EudraCT	European Union Drug Regulating Authorities Clinical Trials (European Clinical Trials Database)
FIH	first in human
FSH	follicle-stimulating hormone
GCP	Good Clinical Practice
GGT	gamma-glutamyl transferase
GI	gastrointestinal
GLP-1	glucagon-like peptide-1
GLP-1R	glucagon-like peptide-1 receptor
HbA1c	hemoglobin A1c
HBcAb	hepatitis B core antibody
HBsAb	hepatitis B surface antibody
HBsAg	hepatitis B surface antigen
HCVAb	hepatitis C antibody
HIV	human immunodeficiency virus
HR	heart rate
HRT	hormone replacement therapy
IB	Investigator's Brochure

Abbreviation	Term
ICD	informed consent document
ICH	International Council for Harmonisation of Technical Requirements for Pharmaceuticals for Human Use
ID	identification
IMP	investigational medicinal product
$\ln AUC_{\text{inf}}$	natural logarithm of $AUC_{\text{inf}}$
$\ln C_{\text{max}}$	natural logarithm of $C_{\text{max}}$
IND	Investigational New Drug
INR	international normalized ratio
$\text{Log}_e$	natural logarithm
IP	Investigational Product
IPAL	Investigational Product Accountability Log
IRB	Institutional Review Board
IV	Intravenous(ly)
K	Proportionality constant for Bedside and Modified Schwartz Equations (kidney function)
$k_{\text{el}}$	terminal phase rate constant
KDIGO	Kidney Disease Improving Global Outcomes
LBBB	left bundle branch block
LFT	liver function test
MCH	mean corpuscular hemoglobin
MCHC	mean corpuscular hemoglobin concentration
MCV	mean corpuscular volume
MEN2	multiple endocrine neoplasia type 2
MoA	mechanism of action
MTC	medullary thyroid cancer
MQI	medically qualified individual
NA	not applicable
NIMP	noninvestigational medicinal product
NOAEL	no-observed-adverse-effect level
OATP	organic anion transporting polypeptide
PCRU	Pfizer Clinical Research Unit
PD	pharmacodynamic(s)
PE	physical examination
PI	principal investigator
PK	pharmacokinetic(s)
PO	oral
PPI	proton pump inhibitor
PSSA	Pfizer's Serious Adverse Event Submission Assistant
PT	prothrombin time
PVC	premature ventricular contraction/complex
QD	once daily
QTc	corrected QT interval

Abbreviation	Term
QTcF	QTc corrected using Fridericia's formula
QTL	quality tolerance limit
qual	qualitative
RBC	red blood cell
RNA	ribonucleic acid
SAE	serious adverse event
SAP	Statistical Analysis Plan
SARS-CoV-2	severe acute respiratory syndrome coronavirus 2
Scr	serum creatinine
Scys	serum cystatin C
SoA	schedule of activities
SOC	System Organ Class
SOP	standard operating procedure
SRSD	Single Reference Safety Document
SUSAR	Suspected Unexpected Serious Adverse Reaction
$t_{1/2}$	terminal half-life
T2DM	Type 2 diabetes mellitus
T bili	total bilirubin
TEAE	treatment-emergent adverse event
THC	tetrahydrocannabinol
T max	time for C max
UACR	urine albumin-creatinine ratio
UGT	uridine diphosphate glucuronosyltransferase
ULN	upper limit of normal
US	United States
V z /F	apparent volume of distribution
WBC	white blood cell
WOCBP	woman/women of childbearing potential

1. VERSION HISTORY

Table 1. Summary of Changes

Version/ Date	Associated Protocol Amendment	Rationale	Specific Changes
1 / 19 Jan 2023	Original 30 Nov 2022	N/A	N/A

2. INTRODUCTION

PF-07081532 is an orally administered, potent and selective GLP-1R agonist in development as adjunct to diet and exercise, to improve glycemic control in T2DM, and for chronic weight management in a population that is overweight with co-morbidities or who have obesity.

The purpose of the study is to evaluate the relative bioavailability following oral administration of 2 formulations of PF-07081532. In Periods 1 and 2, the PK of the formulation projected to be used in future clinical studies (PF-07081532 80 mg immediate release tablet, Formulation B) will be compared with the PK of the current formulation (PF-07081532 20 mg immediate release tablet + 60 mg immediate release tablet, Formulation A) in the fasted state in adult participants who are overweight or obese.

This SAP provides the detailed methodology for summary and statistical analyses of the data collected in Study C3991010.

2.1. Modifications to the Analysis Plan Described in the Protocol

None.

2.2. Study Objectives and Endpoints

Objectives	Endpoints
Cohort 1	
Primary:	Primary:

 To compare the relative bioavailability of PF-07081532 following administration of a single oral dose of Formulation B (Test) compared to Formulation A (Reference) administered in the fasted state to adult participants who are overweight or obese. 	
 Plasma: PF-07081532 AUC_{inf} (as data permit, otherwise AUC_{last}) and C_{max} for Formulations A and B.

Objectives	Endpoints
Secondary:	Secondary:

 To evaluate the safety and tolerability of a single oral dose of PF-07081532 administered in the fasted state to adult participants who are overweight or obese. 	
 Assessment of treatment emergent AEs, clinical laboratory abnormalities, vital signs, ECG parameters.
Other:	Other:

 To determine additional pharmacokinetic parameters of PF-07081532 following administration of a single oral dose of PF-07081532 as Formulation A (Reference) and Formulation B (Test) in the fasted state to adult participants who are overweight or obese. 	
 Additional plasma PK parameters: 
 AUC_{last} CL/F and V_z/F, as data permit T_{max} Half-life (t_{1/2}), as data permit.

2.3. Study Design

This is a randomized, open-label, single dose, 2-period, 2-sequence, crossover study. Participants will be screened for participation in this study within 28 days before dosing in Period 1 to confirm that they meet the inclusion/exclusion criteria for this study. A minimum washout of 6 days between the single 80 mg doses (80 mg immediate release tablet for Formulation B, 20 mg immediate release tablet + 60 mg immediate release tablet for Formulation A) administered in each period will be employed. The expected duration of participation from Screening to the Follow-up telephone contact will be approximately 10 weeks.

Approximately 20 participants will be enrolled to ensure at least 14 evaluable participants with PK data.

Table 2. Randomization Schedule

	Period 1	Period 2
Sequence 1 (N=10)	Formulation A	Formulation B
Sequence 2 (N=10)	Formulation B	Formulation A

Formulation A (Reference) will be administered as PF-07081532 20 mg immediate release tablet + 60 mg immediate release tablet, and Formulation B (Test) will be administered as a PF-07081532 80 mg immediate release tablet.

3. ENDPOINTS AND BASELINE VARIABLES: DEFINITIONS AND CONVENTIONS

3.1. Primary Endpoints

The primary endpoints are the plasma PF-07081532 AUC_{inf} (as data permit, otherwise AUC_{last}) and C_{max} for Formulations A (PF-07081532 20 mg + 60 mg) and B (PF-07081532 80 mg). In addition, the test/reference ratios for AUC_{inf} (as data permit, otherwise AUC_{last}) and C_{max} will be derived with Formulation B as the test treatment and Formulation A as the reference treatment.

3.2. Secondary Endpoints

The secondary endpoints are the safety and tolerability data, discussed in [Section 3.5](#).

3.3. Baseline Variables

Baseline characteristics will be collected according to the schedule of activities (SoA) as specified in the protocol.

3.4. Other Endpoints

Other endpoints include additional plasma PK parameters for formulations A and B of PF-07081532 including AUC_{last} , CL/F , V_z/F , T_{max} , and $t_{1/2}$ as data permit.

Plasma PK parameters of PF-07081532 will be derived (as data permit) from the concentration-time data using standard noncompartmental methods as outlined in Table 3. Actual PK sampling times will be used in the derivation of PK parameters. In the case that actual PK sampling times are not available, nominal PK sampling time will be used in the derivation of PK parameters.

Table 3. Plasma PK Parameters

Parameter	Definition	Method of Determination
AUC_{inf}^a	Area under the concentration-time curve from time zero extrapolated to infinity	$AUC_{last} + (C_{last}^*/k_{el})$, where C_{last}^* is the predicted plasma concentration at the last quantifiable time point from the log-linear regression analysis
AUC_{last}	Area under the plasma concentration-time profile from time zero to the time of the last quantifiable concentration (C_{last}).	Linear/Log trapezoidal method.
C_{max}	Maximum observed concentration	Observed directly from data
T_{max}	Time for C_{max}	Observed directly from data as time of first occurrence

Table 3. Plasma PK Parameters

Parameter	Definition	Method of Determination
$t_{1/2}^a$	Terminal half-life	$\log_e(2)/k_{el}$, where k_{el} is the terminal phase rate constant calculated by a linear regression of the loglinear concentration-time curve. Only those data points judged to describe the terminal log-linear decline will be used in the regression.
CL/F^a	Apparent clearance	$Dose/AUC_{inf}$
V_z/F^a	Apparent volume of distribution	$Dose/(AUC_{inf} \times k_{el})$

a. If data permit.

3.5. Safety Endpoints

The following data are considered in standard safety summaries (see protocol for collection days, baseline assessment, and list of parameters):

- adverse events (AE)
- laboratory data
- vital signs data
- electrocardiogram (ECG) results

3.5.1. Adverse Events

Any adverse events occurring following start of treatment will be considered as treatment emergent adverse event (TEAE). Events that occur during follow-up within the lag time of up to 35 days after the last dose of study intervention will be counted as treatment emergent and attributed to the last treatment taken. The time period for collecting AEs (“active collection period”) for each participant begins from the time the participant provides informed consent.

3.5.2. Laboratory Data

Safety laboratory tests will be performed as described in the protocol. To determine if there are any clinically significant laboratory abnormalities, the haematological, clinical chemistry (serum) and urinalysis safety tests will be assessed against the criteria specified in the sponsor reporting standards. The assessment will not take into account whether each participant's baseline test result is within or outside the laboratory reference range for the particular laboratory parameter.

For both periods, the baseline measurement is the predose measurement on Period 1 Day -1.

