**SoA-Table 1. Study Schedule of Assessment**

Visit Identifier Abbreviations used in this table may be found in Appendix 10 .	Screening	Periods 1 and 2					ET	Follow -Up	Notes
		Day -1 (Period 1 Only)	Day 1	Day 2	Day 3	Day 4			
Days Relative to Day 1	Day -28 to Day -2							28-35 days	
 
All screening should be done <math>\leq</math>28 days before the first dose.
 
Day relative to start of study intervention (Day 1).
 
Follow-up may occur via telephone contact and must occur 28 to 35 days after administration of the final dose of study intervention.
 

Hours After Dose		0	48	72	96				
Blood samples for:									
Clinical laboratory tests after 4-hour fast	X	X					X	X	
 
See Appendix 2 for details of clinical laboratory tests
 
Day 5: Procedures at discharge (Period 2) only.
 

FSH (postmenopausal females only), HBsAg, HBcAb, HCVAb, calcitonin	X								
HIV	X								
Pregnancy test (WOCBP only)	X	X					X	X	
 
Day 5: Procedures at discharge (Period 2) only.
 

CCI			■					■	[REDACTED]
CCI			■					■	[REDACTED]

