### **Diagnostic Assessments:**

8. A positive urine drug test.
9. Using a properly sized and calibrated BP cuff, screening supine BP  $\geq 140$  mm Hg (systolic) or 90 mm Hg (diastolic) following at least 5 minutes of supine rest. If BP is  $\geq 140$  mm Hg (systolic) or  $\geq 90$  mm Hg (diastolic) the BP should be repeated 2 more times and the average of the 3 BP values should be used to determine the participant's eligibility.
10. Baseline 12-lead ECG that demonstrates clinically relevant abnormalities that may affect participant safety or interpretation of study results (eg, QTcF  $>450$  ms, complete LBBB, signs of an acute or indeterminate- age myocardial infarction, ST-T interval changes suggestive of myocardial ischemia, second- or third- degree AV block, or serious bradyarrhythmias or tachyarrhythmias). If the uncorrected QT interval is  $>450$  ms, this interval should be rate-corrected using the Fridericia method only and the resulting QTcF should be used for decision making and reporting. If QTcF exceeds 450 ms, or QRS exceeds 120 ms, the ECG should be repeated 2 more times and the average of the 3 QTcF or QRS values used to determine the participant's eligibility. Computer-interpreted ECGs should be overread by a physician experienced in reading ECGs before excluding a participant.
11. Participants with ANY of the following abnormalities in clinical laboratory tests at screening, as assessed by the study-specific laboratory and confirmed by a single repeat test, if deemed necessary:
  - AST or ALT level  $\geq 1.25 \times$  ULN;
  - Total bilirubin level  $\geq 1.5 \times$  ULN; participants with a history of Gilbert's syndrome may have direct bilirubin measured and would be eligible for this study provided the direct bilirubin level is  $\leq$  ULN;
  - HbA1c  $\geq 6.5\%$ ;
  - Fasting blood glucose  $\geq 126$  mg/dL (7 mmol/L);
  - Calcitonin  $>$  ULN;
  - eGFR  $< 60$  mL/min/1.73 m^2 as calculated by the CKD-EPI equation.

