6.6.2. Laboratory Data

Laboratory data will be listed and summarized by treatment in accordance with the CaPS.

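### Laboratory abnormalities are assessed without regard to baseline status, so pre-existing abnormalities can be counted without distinction from new ones

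*SAP*

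**What the plan says.** SAP Section 3.5.2 says that safety laboratory results will be "assessed against the criteria specified in the sponsor reporting standards". The numeric limits are not reproduced in the SAP or the protocol. The section then sets the rule at issue: "The assessment will not take into account whether each participant's baseline test result is within or outside" the reference range.

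The same section nevertheless defines a baseline: "For both periods, the baseline measurement is the predose measurement on Period 1 Day -1".

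For reporting, SAP Section 6.6.2 says only: "Laboratory data will be listed and summarized by treatment in accordance with the CaPS". It names no shift table, change from baseline or split by baseline status.

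The endpoint served is secondary. SAP Section 2.2 words it as "Assessment of treatment emergent AEs, clinical laboratory abnormalities, vital signs, ECG parameters".

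On timing, the protocol's Schedule of Activities (SoA-Table 1) has clinical laboratory tests at screening, on Day -1 of Period 1, on Day 5 and at early termination. Its note on the Day 5 tests reads "Day 5: Procedures at discharge (Period 2) only".

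**The concern.** The plan collects and defines a pre-dose laboratory value, then sets its range status aside when it decides what counts as an abnormality. That would matter little if everyone entered with in-range values or if a control group absorbed the background rate. Neither is the case. Eligibility tolerates some out-of-range results, and both sequences receive active drug in both periods.

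What is at stake is how one secondary safety endpoint reads. A participant who was already outside the criterion on Day -1 and is unchanged after dosing looks the same in the count as one who became abnormal after dosing. With about 20 participants, each person moves a percentage by 1/20 = 5 points, so one or two carried-over abnormalities would be visible in the table.

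**Working it through.** The documents give no figure for this point, so there is none to reproduce. The check sets the relevant sections side by side and then bounds the effect under stated assumptions.

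**Step 1. Can an out-of-range baseline enter?** Yes, by several routes.
- AST or ALT: exclusion criterion 11 (Protocol Section 5.2) applies only at 1.25 x ULN or higher, so values above ULN but below 1.25 x ULN are admitted.
- Total bilirubin: exclusion applies at 1.5 x ULN or higher, so values above ULN but below 1.5 x ULN are admitted. Participants with a history of Gilbert's syndrome qualify on direct bilirubin, with no stated ceiling on total bilirubin.
- Haematology, urinalysis, creatine kinase and uric acid are in the panel (Protocol Appendix 2, Table 5), but criterion 11 gives no numeric limit for them. Inclusion criterion 2 requires participants to be judged healthy, which is not a requirement that every result be in range.
- Criterion 11 is applied to screening results, up to 28 days before dosing. The analysis baseline is Day -1, so the two values can differ.

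**Step 2. Is there another comparator?** No. There is no placebo or untreated arm (Protocol Section 4.1, Table 3). For completers the only scheduled post-dose panel is Day 5 of Period 2. That leaves the participant's own Day -1 value.

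**Step 3. When is a pre-existing abnormality counted?** Two things must hold: the baseline value meets the sponsor criterion, and it still meets it after dosing. Let p be the share of participants for whom both hold on at least one parameter. The documents do not give p.
- If the criterion for a parameter lies at or above its entry ceiling (for example, an AST/ALT criterion of 1.25 x ULN or more), a value admitted under that ceiling does not meet it, and the parameter contributes about zero.
- If the criterion lies below the ceiling, or there is no ceiling, p can exceed zero.

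**Step 4. Size for n = 20** (about 20 to be enrolled, Protocol Section 4.1). Expected count = n x p. Chance of at least one = 1 - (1 - p)^n, treating participants as independent.

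| Assumed p | Expected count | Chance of at least one |
|---|---|---|
| 0% | 20 x 0 = 0 | 0% |
| 1% | 20 x 0.01 = 0.2 | 1 - 0.99^20 = 18% |
| 5% | 20 x 0.05 = 1 | 1 - 0.95^20 = 64% |
| 10% | 20 x 0.10 = 2 | 1 - 0.90^20 = 88% |
| 20% | 20 x 0.20 = 4 | 1 - 0.80^20 = 99% |

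With 14 participants, the minimum planned as evaluable for pharmacokinetics, assumed shares of 1%, 5%, 10% and 20% give chances of 13%, 51%, 77% and 96%. The safety set is everyone dosed, so 20 is the more relevant number.

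**The case against.** The strongest reply is that this is a presentation choice, openly prespecified, for a descriptive endpoint with no hypothesis test or laboratory decision rule. Counting every post-dose abnormality is over-inclusive, which is a cautious stance for safety screening. Baseline is considered elsewhere. Protocol Appendix 3 mentions worsening from baseline when laboratory findings are judged as adverse events, Appendix 6 has separate thresholds for abnormal liver baselines, and Appendix 7 uses baseline and later kidney values. Laboratory data are also listed, so a reader can compare Day -1 with Day 5 by hand. Finally, the sponsor's reporting standards may already require a baseline split or change-from-baseline display.

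Much of this stands, and it limits the harm. It does not repair the tabulated count. The adverse-event route depends on investigator judgement, and the liver and kidney rules cover only those tests. A listing leaves the split to be reconstructed after the data are seen. Whether the sponsor standards already supply the display cannot be confirmed or excluded from the documents.

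Three stronger readings are tempting and should be resisted.
- A reader might infer that pre-existing abnormalities are reported as on-treatment findings. The SAP does not call them that. In SAP Section 2.2 the term treatment emergent is attached to adverse events, with laboratory abnormalities listed separately.
- A reader might infer that the admitted AST/ALT and bilirubin values will inflate the count. They may add nothing if the unseen criteria lie at or above the entry ceilings.
- A reader might infer that the count of participants with a normal baseline should carry the safety conclusion. That would drop participants whose abnormal baseline worsens, whom Appendices 3 and 6 deliberately keep in view.

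**Conclusion.** The point holds in a limited form. The planned assessment can count old and new abnormalities without distinction, although the value needed to separate them is already collected and defined. The effect runs from none to a few of 20 participants. It rests on an assumed share with a qualifying, persisting baseline abnormality, and on sponsor criteria that are not in the documents. The upper rows of the table are illustrations, not estimates, and the zero row is possible.

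The documents do not show that the count will be overstated, only that it could not be read as newly arising abnormalities. A split by baseline would not establish that the drug caused a finding, because there is still one scheduled post-dose panel for completers and no control. It would show which findings arose or worsened after Day -1. This is a minor, optional improvement.

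**What to change.** Keep the current rule and table. Add to SAP Sections 3.5.2 and 6.6.2 a second tabulation that applies the same abnormality criteria, split by Day -1 status:
- normal on Day -1 and abnormal after dosing (newly abnormal);
- abnormal on Day -1 and abnormal after dosing, shown separately as worsened or not worsened from the Day -1 value.

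State in the SAP, before the data are reviewed, what Day -1 status is judged against (the existing sentence already refers to the laboratory reference range) and how worsening is defined. Base the safety interpretation on newly abnormal and worsened values together, not on the normal-baseline group alone. If the sponsor's reporting standards already require such a display, a sentence in Section 6.6.2 naming it would be enough.

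The cost is one extra table from data already collected, with small denominators in each stratum. No additional sampling, change to eligibility or change to the primary analysis is needed.
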